11.4 Technical complaints and technical complaint samples

11.4.1 Reporting of technical complaints

All technical complaints on any of the following products:

- N8-GP 500 U/vial
- N8-GP 2000 U/vial
- Sodium Chloride 0.9 % vial
- Novo Nordisk trial injection kit

which occur from the time of first usage of trial product until the time of the last usage of the product, must be collected and reported to Customer Complaint Center, Novo Nordisk.

Contact details (fax, e-mail and address) are provided in Attachment I to the protocol.

The investigator must assess whether the technical complaint is related to any AE(s), SAE(s) and/or MESI(s).

Technical complaints must be reported on a separate technical complaint form for each product listed. If the technical complaint involves more than one batch, lot number or more than one DU, a technical complaint form for each batch, lot number or for each DU must be completed.

The investigator must complete the technical complaint form in the eCRF within the following timelines of the trial site obtaining knowledge of the technical complaint:

- Technical complaint assessed as related to an SAE within 24 hours
- All other technical complaints within 5 calendar days

If the eCRF is unavailable or when reporting a technical complaint that is not patient related, the information must be provided on a paper form by fax, e-mail or courier to Customer Complaint Center, Novo Nordisk, within the same timelines as stated above.

11.4.2 Collection, storage and shipment of technical complaint samples

The investigator must collect the technical complaint sample and notify the monitor **within 5 calendar days** of obtaining the sample at trial site. The monitor must coordinate the shipment to Customer Complaint Center, Novo Nordisk (the address is provided in Attachment I) and ensure that the sample is sent as soon as possible. A print or copy of the technical complaint form must be sent with the sample.

The investigator must ensure that the technical complaint sample contains the batch, lot number and, if available, the dispensing unit number (DUN).

Protocol v 1 | 82 of 114

Protocol Date: 04 November 2013 Novo Nordisk Version: 1.0

If the technical complaint sample is unobtainable, the investigator must specify on the technical complaint form why it is unobtainable.

Storage of the technical complaint sample must be done in accordance with the conditions prescribed for the product). The shipment of the technical complaint sample should be done in accordance with the same conditions as for storage, see Section 9

11.5 Precautions and/or overdose

As with any protein injected i.v. hypersensitivity reactions may occur. The possible events include rash, pruritus, fever, nausea, headache, vomiting and changes in blood pressure. If any of these events are suspected, further N8-GP administration should be stopped and the patient should receive treatment as appropriate according to the hospital practice and guidelines.

If an overdose of N8-GP is suspected further N8-GP administration should be stopped prior to any further N8-GP administration and the patient should receive treatment as appropriate according to hospital practice and guidelines.

11.6 Committees related to safety

11.6.1 Novo Nordisk safety committee

Novo Nordisk will constitute an internal safety committee to perform ongoing safety surveillance of N8-GP. The safety committee works according to a written guideline and will meet regularly to discuss and evaluate the overall safety for N8-GP for this trial and all other N8-GP trials. The Novo Nordisk safety committee can take action with regard to the patient safety for the trial based upon observations of the overall information for N8-GP. Pre-defined rules for setting the enrolment on hold is described in Section 11.6.2.

The safety committee might meet to evaluate data at any time point during the conduct of the trial if deemed necessary.

11.6.2 Rules for putting the enrolment on hold

A safety analysis will be performed to evaluate the development of inhibitor at the following predefined time point:

• after the first 25 patients have been to visit 6 (20-25 exposure days)

The expected rate of inhibitors is about 30% in PUPs with severe haemophilia A.⁴ In case of confirmed FVIII inhibitor formation in 12 or more of all exposed patients, all cases of inhibitor formation will be evaluated by the N8-GP safety committee. During these evaluations, ongoing treatment in the trial will continue, however new patients will not be enrolled in the trial. The

Protocol v 1 | 83 of 114

Protocol Date: 04 November 2013 Novo Nordisk

 Trial ID: NN7088-3908
 Version:
 1.0

 UTN: U1111-1148-1897
 Status:
 Final

 EudraCT No.: 2013-004025-88
 Page:
 84 of 114

evaluation will provide the basis for a decision on any actions required for the trial to allow for continuation of enrolment or decision to terminate the trial, and will be documented in the safety committee meeting minutes.

During the evaluation the safety committee will also evaluate risk factors for inhibitor formation such as ethnicity, family history of inhibitors, FVIII gene mutation type, age at first FVIII treatment, reason for first treatment, treatment duration after first treatment, the details of any surgery (including type of surgery, amount of product used, and outcome), any recent infection and any recent vaccination. Furthermore the time of occurrence of inhibitor formation (after how many exposures) and whether the inhibitor is a high or low titre will be evaluated.

Protocol v 1 84 of 114

04 November 2013 | **Novo Nordisk** Protocol Date: Trial ID: NN7088-3908 Version: 1.0

Final

UTN: U1111-1148-1897 Status: EudraCT No.: 2013-004025-88 Page: 85 of 114

Case report forms 12

Novo Nordisk will provide a system for the electronic case report forms (eCRF). This system and support services to the system will be supplied by a vendor. The activities of this vendor will be under the direction and supervision of Novo Nordisk.

The investigator or delegated person should ensure that all relevant questions are answered, and that no empty data field exists.

If a test or an assessment has not been done and will not be available, or if the question is irrelevant (eg is not applicable), indicate this according to the date entry instructions.

The following will be provided as paper CRF:

1. Hypersensitivity questionnaire

In addition paper AE forms, safety information forms and Technical Complaint forms will be provided. These must be used when access to the eCRF is revoked.

On the paper CRF forms print legibly, using a ballpoint pen. Ensure that all questions are answered, and that no empty data blocks exist. Ensure that no information is recorded outside the data blocks.

If a test or an assessment has not been done and will not be available, indicate this by writing "ND" (not done) in the appropriate answer field in the CRF. If the question is irrelevant (eg is not applicable) indicate this by writing "NA" (not applicable) in the appropriate answer field. Further guidance can be obtained from the instructions in the CRF.

The investigator must ensure that all information derived from source documentation is consistent with the source information. By electronically signing the case book in the eCRF, the investigator confirms that the information in the eCRF including related forms is reviewed, complete and correct.

12.1 Corrections to case report forms

Corrections to the eCRF data may be made by the investigator or the investigator's authorised staff. An audit trail will be maintained in the eCRF application containing as a minimum: the old and the new data, identification of the person entering the data, date and time of the entry and reason for the correction.

If corrections are made by the investigator's authorised staff after the date the investigator has signed the case book, the case book must be signed and dated again by the investigator.

Protocol v 1 85 of 114

Corrections to the data in paper CRFs may only be made by drawing a straight line through the incorrect data and then writing the correct entry next to the data that were crossed out. Each correction must be initialled, dated and explained (if necessary) by the investigator or the investigator's authorised staff.

Corrections necessary after the paper CRFs have been removed from the investigator's trial site must be documented on a data clarification form (DCF) or a monitor-initiated discrepancy form (MIDF).

12.2 Case report form flow

The investigator must ensure that data is recorded in the eCRF as soon as possible, preferably within 5 days after the visit. Once data have been entered, it will be available to Novo Nordisk for data verification and validation purposes.

Site specific eCRF data (in an electronic readable format) will be provided to the trial site before access to the eCRF is revoked. This data must be retained at the trial site.

When the final CTR is available, the data will be archived by Novo Nordisk.

12.3 Electronic diary

Novo Nordisk will provide the patient's parent(s)/LAR(s) with an eDiary for electronic recording of details of their child's prophylaxis administration, bleeding episodes, surgery and treatment hereof, see Sections 8.1.12.1 and 8.6. The eDiary and related support services will be supplied by a vendor working under the direction and supervision of Novo Nordisk.

At visit 2, the patient's parent(s)/LAR(s) will receive the eDiary and they will be trained in the use hereof by the investigator or delegated person. After visit 2 (after 2 EDs) and onwards, data will be entered by the patient's parent(s)/LAR(s) in the eDiary device during home treatment.

During trial site visits, data will be recorded in the eCRF by the trial staff, and should not be entered by the patient's parent(s)/LAR(s) in the eDiary.

The eDiary will be returned by the patient's parent(s)/LAR(s) at the EOT visit.

All data entered will be transferred from the device to an electronic database, where it is kept as a certified copy of the source data. Data entered in the device will upon confirmation of a successful back-up be deleted from the device.

The eDiary will have built in edit checks and reminders, to ensure that all relevant questions are answered.

Protocol v 1 | 86 of 114

eDiary data transferred to the electronic database will be viewable to relevant trial site staff and Novo Nordisk personnel on a secure, password protected web portal.

It is the responsibility of the Investigator to review and thereby ensure the eDiary data quality. Following must be checked as minimum that the eDiary data is complete, consistent and according to the requirements defined in this protocol. Upon review the Investigator must document that the review has taken place and any actions required e.g. retraining of patients.

It must be confirmed by the patient's parent(s)/LAR(s) if missing eDiary data need to be entered and/or if the transferred eDiary data needs to be corrected. This is done by filling in and forwarding a Data Correction Request to the eDiary vendor. An audit trail will be maintained.

Protocol v 1 87 of 114

13 Monitoring procedures

During the course of the trial, the monitor will visit the trial site to ensure that the protocol is adhered to, that all issues have been recorded, to perform source data verification and to monitor drug accountability.

The first monitoring visit will be performed as soon as possible after FPFV and no longer than 4 weeks after. The monitoring intervals will depend on the outcome of the remote monitoring of the eCRFs, the trial site's recruitment rate and the compliance of the trial site to the protocol and GCP. The intervals between monitoring visits must not exceed 12 weeks whilst patients are in the trial.

The monitor must be given direct access to source documents (original documents, data and records). Direct access includes permission to examine, analyse, verify and reproduce any record(s) and report(s) that are important to the evaluation of the trial. If the electronic medical record does not have a visible audit trail, the investigator must provide the monitor with signed and dated printouts. In addition the relevant trial site staff should be available for discussions at monitoring visits and between monitoring visits (eg by telephone).

For all data recorded the source document must be defined in a source document agreement at each trial site. There must only be one source defined at any time for any data element.

All data must be verifiable in source documentation other than the eCRF, except for the following data that may be recorded directly in the eCRF and will then be considered source data:

- Ethnicity
- Race

The patient will only be identified by patient number and the monitor will verify and ensure that the eCRFs and eDiary are completed. Also it must be checked that the eDiary data review has been documented by investigator and that the needed action has been taken, if any

Monitors must review the patient's medical records and other source data (eg the diaries) to ensure consistency and/or identify omissions compared to the eCRF. If discrepancies are found, the investigator must be questioned about these.

A follow-up letter (paper or electronic) will be sent to the investigator following each monitoring visit addressing any action to be taken.

For screening failures: Data for the screening visit must be entered in the eCRF within preferably 3 days after data are available and the Screening Failure Form must be completed. Source data verification is not required except for informed consent, reason for screening failure and for data

Protocol v 1 | 88 of 114

relating to any AEs if applicable. All data entered in the eCRF will be transferred into the trial database.

For withdrawn patients: All data collected in the period the patient participated in the trial will be entered into eCRF.

All information captured during visits to the trial site will be collected in the eCRF. When home treatment is initiated all bleeding episodes and injections with N8-GP occurring outside the trial site should be entered in the eDiary by the patient's parents/LAR (see Section 8.8.3). The completed eDiary is considered source data.

Protocol v 1 89 of 114

UTN: U1111-1148-1897 CONFIDENTIAL Status: Final Page: 90 of 114

14 Data management

Data management is always the responsibility of Novo Nordisk.

Data management may be delegated under an agreement of transfer of responsibilities to another data management unit within Novo Nordisk or an external Clinical Research Organisation (CRO).

Appropriate measures, including encryption of data files containing person identifiable data, will be used to ensure confidentiality of patient data, when they are transmitted over open networks.

Laboratory data from central laboratories will be transferred electronically from the laboratory performing the analyses. In cases where laboratory data are transferred via non-secure electronic networks, data will be encrypted during transfer.

The central and local laboratories will provide laboratory reports to the investigator for storage at the trial site. The laboratory report must be signed and dated by the investigator or delegated person and stored at the trial site as source data.

The patient and any biological material obtained from the patient will be identified by patient number and trial identification number. Appropriate measures such as encryption or leaving out certain identifiers will be enforced to protect the identity of patients in all presentations and publications as required by local, regional and national requirements.

Protocol v 1 | 90 of 114

Protocol Trial ID: NN7088-3908 Date: 04 November 2013 Novo Nordisk
Version: 1.0

15 Computerised systems

Novo Nordisk will capture and process clinical data using computerised systems that are described in Novo Nordisk Standard Operating Procedures (SOPs) and IT architecture documentation. The use and control of these systems are documented.

Investigators working on the trial may use their own electronic systems to capture source data. Novo Nordisk will collect information on the practical use of these systems within the conduct of this clinical trial.

Novo Nordisk will use the Global Haemophilia Network Investigator Portal to distribute and share trial-related documents and information with the participating sites.

The eDiary software and hardware implementation are compliant with the requirements of FDA 21 CFR Part 11 and ICH E6 (EU directive for personal data protection). After trial completion, each trial site will be supplied with long-life CDs. These CDs will contain site-specific patient records including the patient's eDiaries and audit trail including any data additions and corrections made on each form. The eDiary vendor will furthermore retain and securely store copies of all archived documents and data for 15 years or as required by local data retention laws for trial data.

Protocol v 1 91 of 114

04 November 2013 | Novo Nordisk Protocol Date: Trial ID: NN7088-3908 Version: 1.0 CONFIDENTIAL Final

Status:

92 of 114

Page:

UTN: U1111-1148-1897 EudraCT No.: 2013-004025-88

16

Statistical considerations

Novo Nordisk will be responsible for the statistical analysis.

The main statistical reporting of the trial will be performed when 50 patients have completed main phase (minimum 25 weeks) with at least 50 EDs and completed visit 9. EDs during ITI treatment will not count in the determination of when a patient has reached 50 EDs. Data from patients not yet having completed the main phase and data from patients that have entered extension phase at this point will be included up to latest visit prior to this cut-off date. This report will cover all endpoints, and will form the basis for the paediatric indication. The data will be presented for the main phase and for the extension phase separately as well as combined.

Except for the confidence interval for inhibitor rate and for annualised bleeding rate, the evaluation of data will be based on descriptive statistics, i.e. summary tables, listings and figures.

An updated reporting of the trial with supportive data will be performed when 100 patients have had at least 100 EDs. Data from all patients will be included up to latest visit prior this cut-off date. The data will be presented for the main + extension phase and the extended prophylaxis period (beyond 100 EDs) separately as well as combined.

All data, will be reported separately in a final report when the trial is completed.

[figure not shown]

Figure 16–1 Individual patient flow and time periods for trial reporting

Multiple bleeding locations occurring from the same event (e.g., due to a fall) or at the same time point will be counted as one bleeding episode.

of 114 Protocol v 1 92

Protocol Date: 04 November 2013 Novo Nordisk Version: 1.0

All bleeding endpoints will be evaluated based on bleeding episodes treated with N8-GP unless the bleeding was considered clinically insignificant (non-treatment requiring bleeding episode) and the associated treatment given was part of prophylaxis.

Patients initiating ITI treatment will for the statistical analyses be considered like withdrawals and data collected during ITI treatment period will be summarised and reported separately. Evaluation of these data will be considered exploratory only.

If necessary, a statistical analysis plan (SAP) may be written in addition to the protocol, including a more technical and detailed elaboration of the statistical analyses. If created, the SAP will be finalised before the first database lock.

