5.3.6 Treatment of patients with FVIII inhibitors

Approximately 20–30% of PUPs with severe haemophilia A develop inhibitors to infused FVIII rendering use of such replacement therapy ineffective. Patients who develop inhibitory antibodies remain at higher risk for morbidity and mortality associated with recurrent or uncontrolled bleeding events.

The majority of haemophilia patients with inhibitors develop high-titre (> 5 BU) inhibitors, and demonstrate an anamnestic rise in their inhibitor titre when re-exposed to FVIII. In these patients even frequent, high-dose FVIII substitution therapy becomes ineffective in controlling bleeding episodes as the infused coagulation factor products are neutralised by the inhibitor. Administration of FVIII bypassing agents (rFVII or activated prothrombin complex concentrates) becomes necessary for treatment of bleeding episodes.

Treatment of bleeding episodes with by-passing agents, i.e. rFVIIa or APCC according to local standard care, is allowed for patients who develop FVIII inhibitors within this trial. By-passing agents are not considered trial medication.

The ultimate goal of treatment in patients with high-titre inhibitors is to permanently eradicate the inhibitor by immune tolerance induction therapy (ITI), thereby making it possible for the patient to be treated routinely with FVIII replacement therapy. The therapeutic concept is based on long-term uninterrupted high exposure to FVIII in an effort to sufficiently tolerize the immune system. In that state, the clinical responsiveness to FVIII replacement therapy is restored.

Based on the available evidence, all patients with high-titre inhibitors (> 5 BU) should undergo ITI using the same type of product that the patient was using at the time of inhibitor development. This approach is supported by an international expert panel which concurred with treatment guidelines which recommend that ITI should be conducted with the same concentrate as the one against which antibodies were developed. This should ensure successful tolerance induction and reduce the risk of further inhibitor development to new molecules. It may therefore be expected that N8-GP will be favourable over the use of commercially available FVIII products for ITI in patients who developed FVIII inhibitors within this trial.

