16.3 Primary endpoint

The primary endpoint is a safety endpoint defined as incidence of inhibitory antibodies against FVIII.

The rate of inhibitory antibodies will be reported and a 1-sided 97.5% upper confidence limit will be provided based on an exact calculation for a binomial distribution. For the calculation of the rate the numerator will include the patients with inhibitors, while the denominator will include all patients with a minimum of 10 exposure days plus any patient with less than 10 exposure days but with inhibitors.

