16.4.2.3 Incidence of high titre inhibitors

The rate of high titre inhibitors (defined as inhibitor titre > 5BU) will be reported similar to the primary endpoint

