5.3.6 Treatment of patients with FVIII inhibitors

Patients who develop FVIII inhibitors during this trial may receive N8-GP and/or Treatment of bleeding episodes with by-passing agents, e.g. i.e. rFVIIa or APCC for treatment of bleeding episodes according to local standard care is allowed for patients who develop FVIII inhibitors within this trial. However, N8-GP dose levels used should not exceed 75 U/kg as a single dose and not exceed 200 U/kg as a maximum 24 hour dose. Treatment with FVIII concentrates other than N8-GP is not allowed. By-passing agents are not considered trial medication.

The ultimate goal of treatment in patients with high-titre inhibitors is to permanently eradicate the inhibitor by immune tolerance induction therapy (ITI), thereby making it possible for the patient to be treated routinely with FVIII replacement therapy again. The therapeutic concept is based on long-term uninterrupted high exposure to FVIII in an effort to sufficiently tolerise the immune system. In that state, the clinical responsiveness to FVIII replacement therapy is restored.

Novo Nordisk plans that Patients who develop inhibitors, within this trial, will be offered continued treatment with N8-GP, including ITI for a maximum of 24 months. ITI with N8-GP will not be initiated until Novo Nordisk has reviewed the clinical data available after completion of the N8-GP pivotal and surgery trial (pathfinderTM2 and pathfinderTM3), and of the paediatric PTP trial (pathfinderTM5) data needed for opening the paediatric PUP trial according to EMA requirements.

It is expected to use a N8-GP dosing regimen for ITI similar to local standard care/guidelines applied for ITI with marketed FVIII products. For each individual patient, ITI regimens with N8-GP would have to be reviewed by the investigator every month, and more formally reviewed every 3 months by Novo Nordisk.

If patients with (usually low titre) inhibitors respond well to treatment with N8-GP then the patient can continue the prophylaxis. These patients can still start ITI treatment within 6 months after the

Protocol Amendment
Trial ID: NN7088-3908

CONFIDENTIAL

Date: 20 March 2015 | Novo Nordisk
Version: 2.0

UTN: U1111-1148-1897 CONFIDENTIAL Status: Final Page: 14 of 41

confirmatory inhibitor test. If the inhibitor is still present (BU>/=0.6) at 6 months after the confirmatory test the patient must start ITI or withdraw from the trial.

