5.3.6.1 ITI therapy with N8-GP

Patients who develop inhibitors, within the pathfinderTM6 trial, will be offered continued ITI treatment with N8-GP for a maximum of 24 months. ITI therapy with FVIII concentrates other than N8-GP is not allowed within the trial. It may also be decided by the Investigator and/or parent/legal representative to withdraw the patients who developed developing FVIII inhibitors.

Patients will be evaluated after 12 months of ITI treatment, based on the level of inhibitors. If inhibitors are still positive after 12 months, but the decline from peak titre level is \geq 20%, ITI may be continued for a the total maximum period of 24 month in total.

If needed and decided by the Investigator, the initiation of the ITI can be delayed but it has to start within 6 months from the time of diagnosis of inhibitor. Inhibitor patients that commence ITI with N8-GP will follow an alternative treatment regimen and visit schedule (see Section 8.1.11).). For each individual patient, ITI regimen with N8-GP will need to be reviewed by the investigator every month, and formally reviewed every 3 months by Novo Nordisk.

The used N8-GP dosing regimen is at the discretion of the investigator, but a N8-GP dosing regimen similar to the local standard of care applied for ITI with marketed FVIII products is recommended. However, daily N8-GP dose levels used for ITI should not exceed 75 U/kg as a single dose and not exceed 200 U/kg as a maximum 24 hour dose.

The FVIII inhibitor level will be evaluated continuously in all patients that receive N8-GP for ITI. If the inhibitor disappears during the ITI (see Section 8.4.2.2), the patient should resume prophylaxis treatment as recommended in Section 5.3.2. Patients will be evaluated after 12 months and 24 months of ITI treatment, based on the level of inhibitors, within the predefined specifications of withdrawal, see Section 6.4. If inhibitors are still positive after 12 months, but the decline from peak titre level is $\geq 20\%$, ITI may continue for a maximum period of 24 month in total. For patients still with positive inhibitors after 12 months ITI, continued trial participation will be evaluated by the investigator and sponsor based on the level of inhibitors, within the predefined specifications of withdrawal criteria 8, see Section 6.4. However, if the inhibitor persists after 24 months of ITI, the patient will be withdrawn from the trial.

EudraCT No.: 2013-004025-88

 Protocol Amendment
 Date:

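### Section 16 treats ITI starters like withdrawals and writes no exception for the high-titre rate, so applying it leaves out a first confirmed titre above 5 BU during ITI.

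*Combined protocol and SAP*

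**What the plan says.** The rule is in the opening part of Section 16 (Statistical considerations): "Patients initiating ITI treatment will for the statistical analyses be considered like withdrawals and data collected during ITI treatment period will be summarised". Those data are to be presented apart from the main results, and the next sentence makes their evaluation exploratory only.

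The high-titre endpoint is defined in Section 4.2.2 as the incidence of confirmed titres above 5 BU and is marked for public posting. Section 16.4.2.3 adds only this: "The rate of high titre inhibitors (defined as inhibitor titre > 5BU) will be reported similar to the primary endpoint". Section 16.3 takes patients with inhibitors as the numerator. For the other part of the fraction it says: "the denominator will include all patients with a minimum of 10 exposure days plus any patient with less than 10 exposure days but with inhibitors". Neither section mentions ITI.

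On who may start ITI, Section 5.3.6.1 (Amendment 2) reads: "Patients who develop inhibitors, within the pathfinderTM6 trial, will be offered continued ITI treatment with N8-GP for a maximum of 24 months". Section 5.3.6 (Amendment 2) adds: "If the inhibitor is still present (BU>/=0.6) at 6 months after the confirmatory test the patient must start ITI or withdraw". Neither limits ITI to titres above 5 BU. Under Amendment 8, ITI may continue after LPLV, and Sections 16 and 16.5 then provide for an addendum to the final report.

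**The concern.** High-titre incidence is a key secondary safety endpoint in a trial whose primary objective is immunogenicity. A patient whose inhibitor is low-titre when ITI starts and who first passes 5 BU during ITI has the outcome that this endpoint is meant to capture. If Section 16 is applied as written, that titre appears only in the exploratory ITI summary, and the patient enters the posted rate as a non-case. The error runs in one direction: the rate can only be too low. If another analyst reads the endpoint definition as overriding the general rule, the same data give a higher rate. Nothing says whether the addendum for patients still in ITI at LPLV updates the rate.

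**Working it through.** The plan attaches no figure to this rule, and Section 16.1 states that no formal sample size calculation was made, so there is nothing to reproduce. The check is whether the case can occur, and what each occurrence does to the rate.

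**Can it occur?**

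1. *Entry.* A patient at or above 0.6 BU and at or below 5 BU may start ITI and, if the inhibitor persists at 6 months, must start it or leave (Sections 5.3.6 and 5.3.6.1, Amendment 2).
2. *Measurement.* Section 8.1.11 lists inhibitor sampling among the assessments recommended at ITI visits.
3. *Rise.* Section 5.3.6 says "The majority of haemophilia patients with inhibitors develop high-titre (> 5 BU) inhibitors" and that they "demonstrate an anamnestic rise in their inhibitor titre when re-exposed to FVIII". It also describes ITI as long-term high exposure. The rise is described for patients who become high-titre, so this makes a crossing plausible and says nothing about its frequency.
4. *Counting.* For withdrawn patients, Section 6.4 allows use of data from before withdrawal. Treated like a withdrawal, the patient contributes only pre-ITI titres to the high-titre rate. The patient stays in the denominator, because Section 16.3 keeps every patient with an inhibitor there.

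**What is its size?**

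Inputs:
- Denominator n = 50, for illustration. Fifty is the exposure-day target for the main report; the Section 16.3 denominator will differ. No figures are given for 100 patients, because Amendment 8 dropped that milestone.
- Inhibitor proportion: 20 to 30% (Section 5.3.6); about 30% (Section 11.6.2).
- More than half of inhibitor patients are high-titre (Section 5.3.6), assumed here to be reached before ITI.

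At 30%: 0.30 × 50 = 15 inhibitor patients, and the smallest majority is 8. At 20%: 0.20 × 50 = 10, and the smallest majority is 6.

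The rate is x/n. The exact one-sided 97.5% upper limit is the value p at which P(X ≤ x | n, p) = 0.025, that is, the 0.975 quantile of Beta(x + 1, n − x).

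| First crossings during ITI | 30% case: rate (upper limit) | 20% case: rate (upper limit) |
|---|---|---|
| None, or all left out | 8/50 = 16.0% (29.1%) | 6/50 = 12.0% (24.3%) |
| One, counted | 9/50 = 18.0% (31.4%) | 7/50 = 14.0% (26.7%) |
| Two, counted | 10/50 = 20.0% (33.7%) | 8/50 = 16.0% (29.1%) |

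Each patient moves the rate by 1/50 = 2 points and the upper limit by 2.3 to 2.4 points in these cases. The ceiling is the number of remaining low-titre patients: 15 − 8 = 7, or 10 − 6 = 4. Reaching it would require every one of them to start ITI and first pass 5 BU there, so it is not an estimate.

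**Minor point: the ITI outcome scale.** In Section 5.3.6.1 (Amendment 3), *partial success* needs a titre reduced to 5 BU or less plus clinical effect. *Failure* lists two items: no success or partial success within 24 months, and a decrease below 20% after one year. Suppose the two items are alternatives and the decrease is taken from peak, as the continuation rule does ("If inhibitors are still positive after 12 months, but the decline from peak titre level is" at least 20%). A peak P above 5 BU and a one-year titre T then meet both categories when T > 0.8P and T ≤ 5, which requires P < 5/0.8 = 6.25 BU. Example: 6 to 5 BU is a fall of 1 − 5/6 = 16.7%.

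**The case against.** The strongest reply is that the exclusion is never stated for this endpoint. Section 4.2.2 sets no time limit, the Section 16.3 numerator is simply patients with inhibitors, and the safety set in Section 16.2 is everyone exposed. This stands in part. A reader might infer that the plan definitely drops these titres, and the documents do not support that, because they allow both readings. But counting them requires an exception to the Section 16 rule that nobody has written.

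A reader might also infer that high-titre cases are concealed. They are not: ITI data are still summarised, confirmed inhibitors are serious adverse events (Section 11.1), and no test or decision threshold depends on the high-titre rate. Nor does the primary endpoint suffer, since these patients already count as inhibitor-positive before ITI.

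Keeping titres measured under ITI apart is a defensible choice, as Section 5.1 calls inhibitor patients a separate cohort. That supports showing the pre-ITI version, but does not support leaving the choice unstated.

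Amendment 3 reprints the Section 16 sentence, but its strike-through is lost in the text available, so it is not independent confirmation. Its rationale does not mention removing the rule. Section 16 allows for a separate SAP, which could settle the matter; none is in the text supplied.

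On the ITI scale, a reader might infer that the overlap is certain. If the two failure items must both hold, it disappears, and the scale itself does not say that the decrease is measured from peak.

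**Conclusion.** The concern holds as a general rule without a needed exception. Applied as written, it removes a first confirmed titre above 5 BU during ITI from the high-titre numerator while keeping the patient in the denominator; a rival reading exists, so the reported rate depends on the analyst. The bias can only be downward, by 2 percentage points per patient at an assumed denominator of 50. The number affected cannot be derived from the documents and may be zero. The conclusion rests on the Section 16 rule having survived Amendment 3 and on no SAP having resolved it. The correction is worth making because the endpoint is a posted safety rate. The overlap in the ITI outcome scale is conditional and optional to address.

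**What to change.** Change analysis wording only; no treatment or withdrawal rule is altered.

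- **Section 16.4.2.3 (or the SAP).** State, as an exception to the Section 16 rule, that a patient counts as high-titre if a central-laboratory titre above 5 BU, confirmed by a second consecutive central-laboratory titre above 5 BU, occurs at any time from first N8-GP dose to last trial visit, including available ITI samples. The confirmation clause is needed because Sections 3.3 and 8.4.2.2 define confirmation only for a positive inhibitor test, not for passing 5 BU.
- **Sensitivity analysis.** Report the rate using the pre-ITI classification.
- **Addendum.** State that it updates the high-titre rate for patients still in ITI at LPLV.
- **Section 16.4.2.7 (optional).** Give an order of precedence for reporting, so that each patient falls in one ITI outcome category.

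The cost is a few sentences, with no required new samples. The rate may be slightly less favourable. ITI assessments are only recommended (Section 8.1.11), so some peaks or confirmatory titres may be missed; the pre-ITI version guards against over-reading an incomplete series.
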